10.3.1 Elevated liver function tests

A listing of subjects with elevated liver function results will be provided. This listing will include subjects who potentially meet Hy’s Law at least 1 time during exposure. Potential Hy’s Law is defined as a subject with AST or ALT $\geq 3x$ upper limit of normal and total bilirubin $\geq 2x$ upper limit of normal where ALP < 2 at the same visit.

For all subjects potentially meeting Hy’s Law, the ratio of hepatocellular to cholestatic values will be calculated using the following formula and included in the listing:

$$nR = \max(\text{ALT} / \text{ULN}, \text{AST} / \text{ULN}) / (\text{ALP} / \text{ULN}), \text{ where ULN is the upper limit of normal}$$

Potential cholestatic injury is defined as a ratio of hepatocellular to cholestatic values ≤ 2 , potential mixed hepatocellular/cholestatic injury is defined as values > 2 and < 5 , and potential hepatocellular injury is defined as values ≥ 5 .

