6.3.1 Potential drug-induced liver injury IMP discontinuation criteria

Subjects with potential drug-induced liver injury (PDILI) must be assessed to determine if IMP must be discontinued. In addition, all concomitant medications and herbal supplements that are not medically necessary should also be discontinued.

The PDILI criteria below require immediate and permanent discontinuation of IMP:

- Subjects with either of the following:
 - ALT or AST $\geq 5xULN$
 - ALT or AST $\geq 3xULN$ and coexisting total bilirubin $\geq 2xULN$

The PDILI criterion below requires immediate discontinuation of IMP:

- Subjects with ALT or AST $\geq 3xULN$ who exhibit temporally associated symptoms of hepatitis or hypersensitivity. Hepatitis symptoms include fatigue, nausea, vomiting, right upper quadrant pain or tenderness. Hypersensitivity symptoms include fever (without clear alternative cause), rash, or eosinophilia (ie, $>5\%$).

If a nondrug-related cause for the symptoms can be confirmed, these subjects may resume IMP administration after discussion with the responsible UCB physician, but only when the requirements for rechallenge with IMP as provided in [Section 11.6.1.2](#) are followed.

The PDILI criterion below allows for subjects to continue on IMP at the discretion of the investigator.

- Subjects with ALT or AST $\geq 3xULN$ (and $\geq 2x$ baseline) and $<5xULN$, total bilirubin $<2xULN$, and no eosinophilia (ie, $\leq 5\%$), with no fever, rash, or symptoms of hepatitis (eg, fatigue, nausea, vomiting, right upper quadrant pain or tenderness).

Evaluation of PDILI must be initiated as described in [Section 11.6.1](#). If subjects are unable to comply with the applicable monitoring schedule, IMP must be discontinued immediately.

Investigators should attempt to obtain information on subjects in the case of IMP discontinuation to complete the final evaluation. Subjects with PDILI should not be withdrawn from the study until investigation and monitoring are complete. All results of these evaluations and observations, as well as the reason(s) for IMP discontinuation and subject withdrawal (if applicable), must be recorded in the source documents. The eCRF must document the primary reason for IMP discontinuation.

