11.6.1.4 Follow-up evaluation

Potential drug-induced liver injury events require follow-up monitoring as described in [Table 11–3](#). Monitoring should continue until liver chemistry values normalize, stabilize, or return to baseline. Determination of stabilization is at the discretion of the investigator in consultation with the hepatologist (as applicable) and UCB responsible physician, as needed.

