10.1 Extent of exposure

The duration of exposure will be calculated as (date of last patch removal – date of first patch application + 1 day).

All derivations of rotigotine doses given below are nominal doses, i.e., include placebo patches in the rotigotine 2mg/24h or placebo arm.

The final dose level ('final dose') is defined as the dose administered at the start of the Maintenance Period (i.e., at Visit 6) and intended to be used during the Maintenance Period. If the subject down titrates to the previous dose during the Titration Period and continues on that dose at Visit 6, then the back-titrated dose level is the 'final dose'.

The determination of the dose of longest duration is based on the entries given in the drug dosing log of the eCRF. The duration of a single dose will be calculated as the sum of the durations of each dosing interval with intake of the respective dose whereas the duration of each dosing interval will be calculated as (end date – start date + 1).

Where more than one dose has the same 'longest duration', the highest dose will be selected. For subjects who dropped out during the Titration Period, the last applied dose during the Titration Period will be used as dose of longest duration. If the dose of longest duration is 0mg/24h, but the subject was exposed at least once to active drug, the minimum active dose will be utilized.

Summary statistics will be presented for the following variables:

- Duration of exposure (days)
- Final dose (mg/24h) at the start of Maintenance (0 mg/24h, 1 mg/24h, 2 mg/24h and 3 mg/24h)
- Dose of longest duration (0 mg/24h, 1 mg/24h, 2 mg/24h and 3 mg/24h)

A listing of patch adhesiveness findings, including date and time of detachment, location and side of body, percent adherence and kit number will be provided.

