10.2 Adverse events

Adverse events will be documented throughout the entire study on an ongoing basis. TEAEs are defined as events that started during the Treatment Period or within 30 days following the end of the Treatment Period (i.e., on or after the date of first patch application and within 30 days following the date of last patch removal) or any unresolved event already present before administration of treatment that worsens in intensity following exposure to the treatment. For AEs with a partial or missing start date, the imputation rules as described in [Section 4.2.2](#) will be applied.

Adverse events with a missing start date are defined as treatment-emergent if the end date of the AE is not on or before the date of first patch application.

An AE with action taken regarding study medication reported on the AE page of the eCRF as “drug permanently withdrawn” will be regarded as an AE leading to discontinuation of study medication.

Adverse events which have the question “Serious Adverse Event?” answered “yes” or missing are considered serious.

Treatment emergent AEs will be tabulated by MedDRA SOC, High Level Term (HLT) and PT. The number and percentage of subjects experiencing each event at least once will be summarized in addition to the number of events. In summaries of TEAEs by relationship and intensity, respectively, the number of events will not be presented.

All summaries will be sorted alphabetically by SOC and HLT and by frequency of events (PT) in the total rotigotine group within HLTs. If there is more than one PT with the same frequency in the total rotigotine group these events will be sorted alphabetically.

An overview of the incidence and frequency of all TEAEs, serious TEAEs, TEAEs leading to discontinuation of study medication, related TEAEs, severe TEAEs, all deaths and TEAEs leading to death will also be provided.

The following tabular summaries will be presented also.

- TEAEs
- TEAEs by intensity
- TEAEs by maximum intensity
- TEAEs by relationship to study medication per the Investigator
- Serious TEAEs
- Serious TEAEs by Relationship to study medication per the Investigator
- non-serious TEAEs above reporting frequency threshold of 5%

Individual subject data listings will be presented for all AEs.

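### SAP 10.3.1 flags potential Hy's Law cases only during exposure, so a subject who first qualifies after the patch is stopped gets no flag and no nR value

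*SAP*

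**What the plan says.** SAP 10.3.1 opens broadly: "A listing of subjects with elevated liver function results will be provided". It then says that the listing includes subjects who potentially meet Hy's "Law at least 1 time during exposure". The criteria are ALT or AST at least 3xULN, total bilirubin at least 2xULN and ALP below 2, all "at the same visit". For these subjects the SAP adds nR, the ratio that sorts a case as cholestatic, mixed or hepatocellular.

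SAP 10.1 counts exposure from first patch application to last patch removal. SAP 3.2.1.2 sets removal at one day after the last application.

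Protocol 11.1.1.3 defines potential Hy's Law by the same transaminase and bilirubin limits, coexisting, without ALP at or above 2xULN. It does not require the subject to be on drug, and every such case is to be reported as an adverse event of special interest.

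Protocol 6.3.1 introduces two triggers with "The PDILI criteria below require immediate and permanent discontinuation of IMP": ALT or AST at least 5xULN, and ALT or AST at least 3xULN with bilirubin at least 2xULN. A third trigger, at least 3xULN with symptoms of hepatitis or hypersensitivity, also stops the drug at once, with resumption possible. Table 11-3 sets liver chemistry at least twice weekly after a stop, and Protocol 11.6.1.4 adds: "Monitoring should continue until liver chemistry values normalize, stabilize, or return to baseline".

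SAP 10.2 counts treatment-emergent adverse events up to and "within 30 days following the date of last patch removal".

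**The concern.** Two of the protocol's stopping triggers act before bilirubin has reached 2xULN. Once they do, the tests that would show whether bilirubin follows are taken off drug. The SAP's flag cannot respond to those tests, although the protocol requires them and its own definition would count them.

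At stake is the one SAP output that identifies potential Hy's Law cases and classifies them by nR. The tabulations in SAP 10.2 include none for events of special interest or for liver injury. If no subject carries the flag, a reader may conclude that no subject met the definition, when one may have met it after the patch came off.

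**Working it through.** The plan states no figure here, so there is none to reproduce. Two checks apply.

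**1. Which samples lie inside the window (completer, nominal days)**

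- Last taper patch applied: Day 110 (Protocol Table 7-3).
- Last patch removal: 110 + 1 = Day 111 (SAP 3.2.1.2).
- Duration of exposure: 111 − 1 + 1 = 111 days (SAP 10.1).
- Scheduled post-Baseline safety laboratory tests: Visit 6 (Day 22), Visit 9 (Day 106) and Safety Follow-Up (Protocol Table 5-1).
- Safety Follow-Up is 30 ± 5 days after the end of taper. Counted from Day 110 it falls on Days 135 to 145, which is 24 to 34 days after removal. Counted from Day 111 it falls on Days 136 to 146, which is 25 to 35 days after removal.
- Adverse event window: 111 + 30 = Day 141 (SAP 10.2).

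So one of the three scheduled post-Baseline samples lies outside the flag's window for anyone who has that visit. Subjects entering RL0007 do not. After a permanent liver-related stop, all later monitoring is outside as well.

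SAP 10.3.1 does not define exposure itself. Reading it as the Treatment Period of SAP 3.2.2 gives no later end, because that period also closes no later than last patch removal.

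**2. The rules applied to assumed sequences**

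These six sequences are illustrations, not trial data. Values are multiples of ULN; ALP is below 2xULN in every sample; the drug is not resumed in B, C or D.

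| | First sample (on drug): ALT / bilirubin | Protocol 6.3.1 | Later sample: ALT / bilirubin | Flag as written | Flag, any sample after first patch, limits met together |
|---|---|---|---|---|---|
| A | 6 / 2.5 | permanent stop | 5 / 3, off drug | yes | yes |
| B | 6 / 1 | permanent stop | 4 / 2.5, off drug | no | yes |
| C | 6 / 1 | permanent stop | 2.8 / 2.5, off drug | no | no |
| D | 4 / 1, symptoms | stop | 3.5 / 2.2, off drug | no | yes |
| E | 4 / 1, no symptoms | may continue | 4 / 2.2, on drug | yes | yes |
| F | 1 / 0.5 | none | 4 / 2.2 at Safety Follow-Up | no | yes |

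The rule as written flags 2 of 6 (A and E). Removing the exposure limit while keeping concurrency flags 5 of 6. C stays unflagged because its two elevations are never present in one sample, so it does not meet the protocol's definition on those samples either. B, D and F do meet the protocol's definition and are lost only through the exposure limit. The counts show which patterns are affected; they do not estimate how often any pattern occurs.

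**The case against.** The strongest reply is that little is hidden. The listing's first sentence covers subjects with elevated liver results, and a subject such as B had ALT 6xULN while on drug, so may appear there anyway. SAP 10.3 lists individual chemistry values with out-of-range results marked, SAP 3.1 puts unscheduled assessments into all listings, and SAP 3.9 says that all data will be listed. Liver-injury events must also be reported as adverse events (Protocol 11.6.1), and all adverse events are listed. This stands. A reader might infer that a case would vanish from the report or that the safety conclusion would change; the documents do not support that. What goes missing is the Hy's Law identification and the nR value. The broad first sentence does not restore them, since it gives no criterion for an elevated result and nR is tied to the Hy's Law group.

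Three further inferences also fail:

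- **That the drug stops at every first signal.** Protocol 6.3.1 lets it continue for an asymptomatic rise of 3x to below 5xULN with bilirubin below 2xULN. If both limits are met in the sample that triggers the stop, that sample is on drug and is flagged (sequence A).
- **That the same-visit condition is itself an error.** It is a fair way to apply the protocol's requirement that the elevations coexist. Pairing peaks from different dates would also flag C, which goes beyond that definition.
- **That most cases would follow the pattern of B.** The documents say nothing about the usual order in which transaminases and bilirubin rise.

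The reply also points out that the study ended early and that this is a descriptive listing with no inference attached. That limits the weight of the point. It does not remove it, because the SAP kept this listing when it cut other analyses.

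**Conclusion.** The point holds for the exposure window. As written, SAP 10.3.1 applies a narrower definition than Protocol 11.1.1.3 and a shorter window than the SAP's own adverse event rule. Two kinds of subject are affected: those stopped for ALT or AST at least 5xULN, or at least 3xULN with symptoms, who meet both limits together only afterwards; and those who first qualify at Safety Follow-Up. Each would lack the flag and the nR value while the underlying values and events remain in other listings.

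The size is small in absolute terms: a labelling gap in one listing of an early-terminated study. The documents give no liver event rates, so an expected number of affected subjects cannot be calculated. The conclusion rests on reading exposure in SAP 10.3.1 as SAP 10.1 counts it, and on the drug not being resumed after the stop.

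**What to change.** In SAP 10.3.1, replace the phrase "at least 1 time during exposure" with wording such as: *at least once at any time after first patch application, including unscheduled liver-injury monitoring samples and the Safety Follow-Up Visit*. Show in the listing whether each qualifying sample was taken on or off drug. Keep the requirement that the limits are met together, but apply it by sample date instead of "at the same visit", so that unscheduled samples are covered.

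Borrowing the 30-day adverse event limit would not be enough. It ends on Day 141 for a completer, while Safety Follow-Up can fall as late as Day 145 or 146, and liver monitoring under Protocol 11.6.1.4 has no fixed end.

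The cost is one sentence, one listing column and a wider data filter, plus perhaps a few extra rows to review. SAP Section 1 allows amendments before database lock.

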10.4 Vital signs, physical findings, and other observations related to safety

10.4.1 Vital signs

Summary statistics of the observed values and changes from Baseline for vital sign parameters (systolic and diastolic blood pressure, and pulse rate) will be presented by visit for supine measurements (after 1 and 5 minutes) as well as standing measurements (after 1 and 3 minutes). Observed values and change from Baseline values will also be presented for the orthostatic reaction after 1- and 3-minutes standing.

Orthostatic hypotension will be assessed using the difference between supine and standing systolic and diastolic blood pressure at each visit. For systolic BP, diastolic BP and pulse, the difference will be calculated using the 5-minute supine values with both the 1 and 3 minute standing values for each parameter, respectively. A drop in systolic BP of ≥ 20 mmHg or a drop in diastolic BP of ≥ 10 mmHg after 1 or 3 minutes in the standing position is indicative of orthostatic hypotension.

Summary statistics of body weight, calculated BMI, temperature, and respiratory rate (including corresponding changes from Baseline) will be presented by visit. Summary statistics of height percentile (based on CDC growth charts at <http://www.cdc.gov/growthcharts>) and including corresponding changes from Baseline will be presented by visit.

A listing of results for vital signs, and body weight, BMI, temperature, respiratory rate, height and height percentile will be provided. A separate listing for orthostatic hypotension will also be provided.

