4.2.2 Other safety variables

- Changes from Baseline (Visit 1) in 12-lead ECGs
- Changes from Baseline (Visit 1) in vital signs (including assessment of orthostasis)
- Changes from Baseline (Visit 1) in laboratory data (hematology, blood chemistry, and urinalysis)
- Changes from Baseline (Visit 1) in hormone status
- Changes from Baseline (Visit 1) in body weight, height, and BMI
- Changes in mMIDI

- Changes in menstrual function for all female subjects

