13.4.1 Safety analyses

Adverse events will be reported in frequency tables as the number and percentage of subjects reporting TEAEs by treatment group. Additionally, frequency tables for serious TEAEs, non-serious TEAEs, TEAEs leading to discontinuation of study medication, TEAEs by intensity and TEAEs by relationship to treatment will be provided by treatment group.

Descriptive statistics on change from Baseline in laboratory data, including hormone status, will be summarized by visit and treatment group. Post-Baseline clinical significant abnormalities will be presented by treatment group.

Vital signs variables and their change from Baseline will be presented using descriptive statistics by visit and treatment group. The number and percentage of subjects meeting orthostatic hypotension criteria will also be presented.

ECG and its change from Baseline will be presented using descriptive statistics by visit and treatment group. The number and percentage of subjects with post-Baseline clinical significant abnormalities will be presented by treatment group.

Body weight, height, and BMI and their change from Baseline will be presented using descriptive statistics by visit and treatment group. Clinically significant values will be reported.

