2.2.2 Safety variables

- Occurrence of treatment emergent adverse events (TEAEs)

- TEAEs leading to withdrawal
- Changes from Baseline in 12-lead electrocardiograms (ECGs)
- Changes from Baseline in vital signs (including orthostatic assessment)
- Changes from Baseline in laboratory data (hematology, blood chemistry, and urinalysis)
- Changes from Baseline in hormone status
- Changes from Screening in body weight, height, and calculated body mass index (BMI)
- Changes from Baseline in Modified Minnesota Impulsive Disorder Interview (mMIDI)
- Changes in menstrual function for all female subjects

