3.9 Changes to protocol-defined analyses

Statistical analysis and generation of tables, figures, subject data listings, and statistical outputs will be performed using SAS Version 9.3 or higher. None of the planned analyses require SAS Version 9.4 and can all be performed on SAS Version 9.3.

Analyses will not be performed as defined in the study protocol due to early study termination. All data will be listed and key summary tables will be produced.

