6 DEMOGRAPHICS AND OTHER BASELINE CHARACTERISTICS

6.1 Demographics

Age will be derived in years applying all rules for missing date imputation as described in [Section 4.2.3](#) as integer $((\text{Date of informed consent} - \text{date of birth}) / 365.25)$.

Weight recorded in pounds (lb) will be converted to kilograms (kg) as $\text{weight}(\text{lb}) * 0.4536 \text{ kg/lb}$.

Height recorded in inches (in) will be converted to height in centimeters (cm) as $\text{height}(\text{in}) * 2.54 \text{ cm/in}$.

The BMI will be calculated as $\text{weight}(\text{kg}) / (\text{height}(\text{m}))^2$.

The following demographics will be summarized for the RS:

- Age (years)
- Age (EudraCT age categories)
- Age (clinicaltrials.gov age categories)
- Gender (Male; Female)
- Racial Group (American Indian/Alaskan Native; Asian; Black; Native Hawaiian or Other Pacific Islander; White; Other/Mixed)
- Ethnicity (Hispanic or Latino; Not Hispanic or Latino)
- Weight (kg)
- Height (cm)
- BMI (kg/m^2)

- BMI (<18.5, 18.5-<25, 25-<30, 30-<35, 35-<40, >=40, Missing)

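### Change in height, a named safety variable, is tabulated only as change in CDC percentile; the protocol's by-visit table of height and its change is replaced without being recorded.

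*SAP*

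**What the plan says.** Protocol 4.2.2 lists "Changes from Baseline (Visit 1) in body weight, height, and BMI" among the other safety variables. Protocol 13.4.1 says how they are to be reported: "Body weight, height, and BMI and their change from Baseline will be presented using descriptive statistics by visit and treatment group".

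The SAP, already cut back for early termination, keeps the variable. SAP 2.2.2 lists "Changes from Screening in body weight, height, and calculated body mass index (BMI").

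SAP 10.4.1 then treats the three measurements differently:
- Weight and BMI stay on their own scales: "Summary statistics of body weight, calculated BMI, temperature, and respiratory rate (including corresponding changes from Baseline) will be presented by visit". Height is not in that sentence.
- For height, the summary is "Summary statistics of height percentile (based on CDC growth charts"), with the change in percentile, by visit.
- Height itself appears only here: "A listing of results for vital signs, and body weight, BMI, temperature, respiratory rate, height and height percentile will be provided".

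Height in cm is tabulated once elsewhere, as a demographic for the Randomized Set (SAP 6.1). SAP 3.9 gives only a general statement about departures from the protocol: "Analyses will not be performed as defined in the study protocol due to early study termination".

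**The concern.** There are two linked problems.

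The first is consistency. The protocol's planned summary of a named safety variable is replaced by a different measure, and the SAP section on changes to protocol-defined analyses does not say so. A reader of the study report who looks for change in height will find no table of it.

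The second is the choice of scale. A percentile is a non-linear transform of standardised height, steep in the middle and flat at both ends. Averaging changes in percentile adds up units of unequal size. If height did shift relative to the reference, the mean percentile change would reflect both the shift and how many subjects in the arm were near the median. Protocol 7.10 names no stratification factor and the study stopped early, so the stature mix of the arms may differ by chance.

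**Working it through.** Neither document gives a figure for height, so there is nothing to reproduce. The check has three parts.

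**1. Which summaries exist after Baseline**

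| Measure | Protocol 13.4.1 | SAP 10.4.1 |
|---|---|---|
| Weight and change | table by visit and arm | table by visit |
| BMI and change | table by visit and arm | table by visit |
| Height (cm) and change | table by visit and arm | height in listing only |
| Height percentile and change | not mentioned | table by visit |

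SAP 3.1 makes summaries by randomized group the default, so the SAP tables are by arm as well. The only real difference is in the height rows.

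**2. How percentile change depends on stature**

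Input: heights normally distributed for age and sex in the reference (assumption). A downward shift of 0.2 SD is used purely as an illustration. With Φ the standard normal distribution function and z the starting height in SD units:

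change in percentile points = 100 × [Φ(z − 0.2) − Φ(z)]

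| Starting z | Percentile before | Percentile after | Change |
|---|---|---|---|
| −2 | 2.3 | 1.4 | −0.9 |
| −1 | 15.9 | 11.5 | −4.4 |
| 0 | 50.0 | 42.1 | −7.9 |
| 1 | 84.1 | 78.8 | −5.3 |
| 2 | 97.7 | 96.4 | −1.3 |

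On the z-score scale the change is −0.2 in every row.

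The pattern does not rest on the size chosen. For a shortfall of 1 cm against the reference, with an assumed height SD of 7 cm, the shift is 1/7 = 0.14 SD. The changes are then −5.7 points from the 50th percentile, −2.7 from the 90th, −1.1 from the 97th and −0.85 from the 3rd. For an SD of 6 to 8 cm, the change at the 50th is 5.0 to 5.2 times that at the 97th and 6.5 to 6.8 times that at the 3rd. The documents give no SD. It sets the size of these numbers, but the dependence on stature holds for any SD.

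**3. What this does to an arm mean**

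Take two hypothetical arms in which every subject loses 0.2 SD:
- All subjects at the median: mean percentile change −7.9.
- Half at z = 0 and half at z = 2: (−7.9 − 1.3)/2 = −4.6.

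The mean z-score change is −0.2 in both. With no shift, Φ(z − 0) − Φ(z) = 0 for every z, so both arms have a mean percentile change of 0. Stature mix rescales a real shift and does not produce one.

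**The case against.** **Early termination was declared.** SAP sections 1 and 3.9 say that the analysis is much reduced and that all data will be listed. That is true, and no height data are lost. It does not explain this item, because a by-visit height table with changes is still produced on another scale, and weight and BMI keep theirs.

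**Percentile has a real merit.** It adjusts for age and sex, which matters at 13 to 17 years, and change in cm does not. If ordinary growth is 1 to 6 cm per year (assumption), then over 120 days, taken as the time from Visit 1 to Visit 9, it is 1 × 120/365.25 = 0.3 cm to 6 × 120/365.25 = 2.0 cm. A mean change in cm can therefore reflect the age and sex mix of an arm. This objection stands, and it is why cm should be read beside a z-score.

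**The illustration is large for a short study.** At an assumed SD of 6.5 to 7.5 cm, 0.2 SD is 1.3 to 1.5 cm. Over 120 days (0.3285 year), that would need complete growth arrest in a subject otherwise growing about 4.0 to 4.6 cm per year. This also stands: 0.2 SD shows the shape of the scale and is not an expected effect.

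**Stronger readings that the documents do not support.**
- A reader might infer that chance imbalance in stature will by itself produce a difference between arms. Part 3 of the working shows that it does not.
- A reader might infer that percentiles at later visits will use age at consent, because SAP 6.1 is where "Age will be derived in years applying all rules for missing date imputation". That derivation is for demographics. SAP 10.4.1 does not say which age is used, and silence is not evidence that age is held fixed.
- A reader might infer that height is collected to detect an effect on growth. Neither document states that purpose, and height is also needed for BMI.
- A reader might infer that height in cm is in no table. Baseline height is tabulated in SAP 6.1; only post-Baseline height and its change are missing.

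**Conclusion.** The point holds as a low-cost improvement. Change in height is a safety variable in both documents. The protocol's table of height and its change is absent from SAP 10.4.1, a percentile table stands in its place, and SAP 3.9 does not record the substitution.

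Mean percentile change is the weaker summary because equal shifts are weighted unequally by stature: about a sixfold range between the median and two SDs above it in the 0.2 SD illustration (7.9/1.3 = 6.1). This rests on a normal reference distribution. The cm versions also rest on an assumed height SD.

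The consequence is small. The table is descriptive, no test or decision depends on it, the study was terminated, and individual heights remain in the listing. It is not a finding that the arms will differ spuriously or that the percentiles will be calculated wrongly.

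**What to change.** In SAP 10.4.1:
- Add height (cm) and its change from Baseline by visit and treatment group, as Protocol 13.4.1 plans.
- Summarise age- and sex-standardised height as a z-score with its change, and state that age is taken at the date of each measurement.
- Keep the CDC percentile in the listing.

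If the table is left as it is, the minimum is a sentence in SAP 3.9 recording that change in height is reported as percentile change.

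The cost is one extra derivation and a few rows in a table that is already planned. No new data are needed, since a CDC percentile already requires age and sex. Where a birth date is partial, SAP 4.2.3 imputes the earliest date, so age at measurement would be approximate for that subject, for percentile and z-score alike. Change in cm is not adjusted for age and sex, and a table note should say that it is to be read with the z-score.
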